16.2 Tumor response rate and duration of response

- 16.21 Tumor response rate is defined as percentage of patients whose objective disease status meets the criteria for RECIST criteria for partial or complete response on two consecutive disease evaluations at least 12 weeks apart.
- 16.22 For those patients who disease had a partial or complete response to treatment on two consecutive disease evaluations at least 12 weeks apart, the duration of treatment response is defined as the time from registration to disease progression.

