- 1.9c11 Clinical Efficacy Endpoint- The expected single agent response rate of pembrolizumab is ~40% in the front line setting and ~25% when given after progression on ipilimumab. Given the small number of patients to be enrolled onto this trial, we will construct a 90% confidence interval for the proportion of patients who have a CR or PR on two consecutive evaluations at least 6 weeks among all the patients enrolled on this trial.
- 1.9c12 Clinical Safety Endpoint - Given the non-overlapping toxicities of pembrolizumab and imiquimod, we expect serious toxicities to occur at a rate similar to each drug individually. For example, pembrolizumab induces serious adverse events in ~10% of patient and imiquimod induces serious adverse events in 1-3% of patients. Therefore we expect ~10-13% of patient to experience a serious adverse event.

1.9d Biomarker Research

One of the largest unmet needs in improving the therapeutic potential of pembrolizumab is identifying reliable predictive biomarkers. In this study, the biomarker research will be exploratory in nature and will include assessing total tumor RNA through RNA seq and PDL1 expression through the use of immunohistochemistry. Attempts will then be made to associate molecular markers with clinical outcomes.

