4.0 Test Schedule

Tests and Procedures	≤28 Days prior to Registration	Day 1 (+/-3 days) of each cycle	End of Treatment	Observation	
				Every 12 (+/- 2) weeks for months 24 thru 36 post registration	at progression
History and Physical Examination, wt, PS	X	X	X	X	X
Height	X				
Adverse Events Assessment	X	X	X	X	X
Pregnancy Test – Urine or Serum –HCG ¹		X ⁶			
CBC w/diff	X ²	X	X	X	X
Renal Profile: Sodium, Potassium, Chloride, Bicarbonate, Creatinine, Bun, Glucose	X ²	X	X	X	X
Albumin, bilirubin total and direct, alkaline phosphatase, total protein, AST, and ALT	X ²	X			
FT4 and TSH	X	X	X		
Disease Evaluation ³	X	X ⁴	X	X	X
Research Tissue Collection ^R		X ⁵			
Photograph of lesions	X	X	X	X	X

1. For women of childbearing potential only. Must be done ≤72 hours prior to registration.

2. ≤14 Days prior to Registration

3. Radiographic tumor imaging assessments must include CT scan, PET/CT, or MRI of the chest, abdomen, and pelvis. CT scan or MRI of the brain with contrast will only be performed if symptoms or signs of CNS metastasis are present. Use same imaging throughout the study.

4. At the completion of cycle 4 (approximately week 12) and then at completion of every 4th cycle (approximately every 12 weeks) thereafter (±7days) until PD.

5. Tissue specimens must be collected and submitted after registration but prior to the start of treatment, at completion of cycles 2 and 4 (approximately weeks 6 and 12).

6. For women of childbearing potential only. Must be done ≤ 72 hours prior to start of treatment. Must be repeated if pre-registration test is > 72 hours prior to the start of treatment.

R Research funded (see Section 19.0)

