9.2 Hypersensitivity reactions

Patients do not require premedication prior to pembrolizumab treatment, as hypersensitivity reactions is not expected. In the unlikely event of a hypersensitivity reaction, treatment with antihistamines, H2 blockers, and corticosteroids is recommended. Patients should be pre-medicated with the typical regimen for subsequent cycles.

9.3 Patients may not enroll in a different clinical study, including Cancer Control studies, in which investigational procedures or agents are being used, while participating in this study.

9.4 Patients must terminate study treatment if they are to receive radiation therapy for palliative reasons as it impacts upon assessing response.

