13.0 Treatment/Follow-up Decision at Evaluation of Patient

- 13.1 Patients who have not had disease progression and have experienced acceptable toxicity are to continue treatment per protocol or a maximum of 2 years (approximately 35 cycles) or until confirmed PD, unacceptable toxicity or refusal.
- 13.2 The first instance in which a patient's disease status meets the RECIST criteria for PD will continue for two additional cycles of treatment per protocol (approximately 6 weeks) and then undergo a disease evaluation. If the initial documented progression is not confirmed by this scan, patients will continue treatment per protocol. If the initial documented progression is confirmed by this scan, patients will go to the event-monitoring phase until death or a maximum of years post-registration.

Exception: Patients who develop PD in the CNS only should discontinue study treatment and go to Event Monitoring.

- 13.3 Criteria for discontinuation of protocol therapy include:
- Disease progression where disease progression is: the development of a new metastatic lesion or an objective status of disease progression (as defined by RECIST criteria) on two consecutive evaluations at least 6 weeks apart (section 13.2). ***Exception: Patients who develop PD in the CNS only should discontinue study treatment and go to Event Monitoring.***
 - Request by patient to discontinue study treatment
 - Unacceptable toxicity
 - Intercurrent illness that would, in the judgment of the investigator, affect assessments of clinical status to a significant degree or require discontinuation of drug
 - Administration of radiotherapy, non-protocol chemotherapy, immunotherapy, biological agents, or an experimental drug during the trial
 - Development of new primary cancer
 - Ineligibility

Patients who discontinue treatment due to intolerability, patient request, physician decision, or inter-current illness preventing further administration of protocol treatment will proceed to event monitoring phase of the trial where patient and disease status until death or a maximum of 3 years post-registration

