16.0 Statistical Considerations and Methodology

16.1 This pilot study will enroll 10 patients to gain preliminary data on the anti-tumor activity and safety profile of the combination of imiquimod and pembrolizumab in patients with unresectable cutaneous melanoma.

If there are no tumor responses documented among these 10 patients, then upper bound of a one-sided 95% confidence interval for the tumor response rate would be 25.9%.

All patients meeting the eligibility criteria who have signed a consent form and have begun treatment will be evaluable for assessment of all of the clinical endpoints.

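### A responder who stops treatment without progression between about weeks 12 and 24 will normally lack the confirming evaluation 16.21 requires, and is by implication a non-responder

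*Combined protocol and SAP*

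**What the plan says.** - **Response definition, 16.21.** A responder must meet "criteria for partial or complete response on two consecutive disease evaluations at least 12 weeks apart".
- **Same endpoint, 1.9c11.** The 90% interval is to be built for patients with "CR or PR on two consecutive evaluations at least 6 weeks among all the patients enrolled". The interval here is 6 weeks, not 12.
- **Scan calendar, 4.0 footnote 4.** Evaluations fall "At the completion of cycle 4 (approximately week 12) and then at completion of every 4th cycle", within 7 days either way. An evaluation is also marked in the End of Treatment column, with no timing relative to the last dose.
- **After an early stop, 13.3.** "Patients who discontinue treatment due to intolerability, patient request, physician decision, or inter-current illness preventing further administration of protocol treatment will proceed to event monitoring". Section 4.1 makes event monitoring 6-monthly until progression and lists no imaging. Under 13.4, the Observation phase, which does have scheduled evaluations, is for patients who complete 2 years of treatment.
- **Scan duration, 11.1.** Scans are to run every 12 weeks until progression is confirmed, with no mention of treatment stopping.
- **Denominator, 16.1.** Eligible, consented patients who "have begun treatment will be evaluable for assessment of all of the clinical endpoints". No rule covers a missing confirmation.

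**The concern.** Together these rules make confirmation depend on staying on treatment for roughly another 12 weeks as well as on the tumor. Section 8.1 permanently discontinues pembrolizumab for most grade 3-4 drug-related events, and 13.3 adds patient request and intercurrent illness. A patient whose tumor has shrunk and stayed shrunk can therefore leave the numerator for a reason unrelated to loss of response, while remaining in the denominator.

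Anti-tumor activity is part of the primary goal in 2.1, and there are 10 patients, so one reclassified patient is visible in the result. The same responder grouping feeds duration of response (16.22) and the responder versus non-responder biomarker comparisons (2.3 and 16.5), so the misclassification carries into those.

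**Working it through.** **Inputs.** n = 10 (16.1). Reference single-agent response rates p of about 40% front line and about 25% after ipilimumab (1.9c11). First evaluation at about week 12, then every 12 weeks, ±7 days (4.0). Confirmation interval 12 weeks (16.21) or 6 weeks (1.9c11). The share q of week-12 responders who stop without progression before a qualifying second scan is **not in the documents** and is assumed.

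**1. The plan's own figure.** Section 16.1 says that with no responses the "upper bound of a one-sided 95% confidence interval for the tumor response rate would be 25.9" percent. The exact bound is 1 − 0.05^(1/10) = 25.89%, so the figure reproduces. It is also the upper limit of a two-sided 90% exact interval, consistent with 1.9c11, and it does not depend on the confirmation interval.

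**2. The calendar.** The nominal first pair is weeks 12 and 24, 12 weeks apart. With the windows, the gap runs from (24 − 1) − (12 + 1) = 10 weeks to (24 + 1) − (12 − 1) = 14 weeks. The earliest qualifying second scan is at week 11 + 12 = 23. A patient still on treatment whose two in-window scans are 10 to under 12 weeks apart also fails the literal 12-week rule.

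**3. A worked patient.** PR at week 12, stops for toxicity, End of Treatment scan at week 18 still PR.
- Under 16.21 the gap is 18 − 12 = 6 weeks: not confirmed. Because evaluations must be consecutive, a literal reading restarts the 12 weeks at the week-18 scan, so the next qualifying scan is at week 30. Section 4.1 lists none.
- Under 1.9c11 the 6-week gap confirms the response.
- Had the End of Treatment scan been at week 15, neither rule would be met without later imaging.

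**4. Effect of one patient.** Exact 90% intervals, n = 10:

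| Responders | Rate | 90% CI |
|---|---|---|
| 4/10 | 40% | 15.0% to 69.6% |
| 3/10 | 30% | 8.7% to 60.7% |
| 1/10 | 10% | 0.5% to 39.4% |
| 0/10 | 0% | 0% to 25.9% |

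Each lost responder moves the estimate 10 points, always downward.

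**5. How often, under an assumed q.** Suppose every responder is in response at week 12 and stopping is independent of response. The expected observed rate is p(1 − q), and the chance of losing at least one responder is 1 − (1 − pq)^10. At q = 5%:
- p = 25%: expected rate 23.75%; chance 1 − (1 − 0.0125)^10 = 11.8%.
- p = 40%: expected rate 38.0%; chance 1 − (1 − 0.02)^10 = 18.3%.

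**6. Against the 6-week rule.** If stops are uniform over weeks 12 to 24 and the End of Treatment scan is done at the stop, half of these patients would still be confirmed under 1.9c11. The expected difference between the two definitions is then pq/2: 0.625 points for p = 25% and 1.0 point for p = 40%. The chance that at least one patient differs is 1 − (1 − 0.00625)^10 = 6.1% and 1 − (1 − 0.01)^10 = 9.6%.

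**The case against.** **A confirming scan is not ruled out.** A reader might infer that such a patient can never be confirmed. The documents do not support that. Section 11.1, read literally, gives a week-24 scan to someone who stopped at week 15. End of Treatment timing is unstated, and 8.1 lets some events be held for up to 12 weeks from the last dose before discontinuation, so some of these evaluations could fall at or after week 24. The windows permit a week 11/23 pair. Section 13.3 mentions disease status in event monitoring without saying how it is assessed. This stands: the claim is about what normally happens, and 11.1 and 4.1 are unclear about imaging after an early stop.

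**Strict is not the same as biased.** If the target is response sustained for 12 weeks, leaving unconfirmed responses out is a conservative definition. This stands in part. The plan does not state that target, and 1.9c11 gives a different one; the shortfall is relative to that. A reader might also infer a shortfall against the single-agent 25% and 40% rates, but the documents do not say how those were confirmed.

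**The probability is unknown.** It is tempting to use the 10-13% serious adverse event expectation in 1.9c11 as q, which gives 22% to 41% for at least one lost responder. That figure has no time window, treatment lasts up to 2 years, and a serious event is not a discontinuation. Spread evenly over 104 weeks with every event causing a stop, it gives 12/104 × 10-13% = 1.2% to 1.5% in the window and a chance of about 3% to 6%. Earlier clustering or other reasons for stopping would raise this.

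**Consequence is limited.** There is no test or success threshold on response, and the 4/10 and 3/10 intervals largely overlap. This stands: the effect is on an estimate and its interval, not on an error rate.

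**Conclusion.** The point holds in limited form. Under the scheduled visits, a patient in CR or PR at about week 12 who stops without progression before about week 24 will normally lack a second consecutive evaluation at least 12 weeks later. Non-responder status is implied by 16.1 and 16.21 together; no explicit rule says so.

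The size per patient is certain: 10 points. The frequency is not. The 12% to 18% rests on an assumed 5% stop rate, independence from response and all responses being present at week 12, and is only illustrative. Against 1.9c11 the loss concerns patients whose End of Treatment scan falls at least 6 but less than 12 weeks after the first.

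The underlying faults are two contradictions, 6 versus 12 weeks (1.9c11 and 16.21) and scans until confirmed progression versus no listed imaging (11.1 and 4.1), plus silence on unconfirmed responses. The correction is worth making because it is cheap and the estimate rests on 10 patients.

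**What to change.** 1. Reconcile the confirmation interval between 1.9c11 and 16.21, choosing one that works with the ±7-day windows. Reconcile 11.1 with 4.1 on imaging after an early stop.
2. State in 16.21 that, for a patient in CR or PR who stops protocol treatment without progression:
   - available imaging after the required interval and before any new anti-cancer therapy, including radiation, counts as the confirming evaluation;
   - an intervening End of Treatment scan still showing CR or PR does not restart the interval;
   - this imaging is collected in event monitoring.
3. Report the unconfirmed best overall response rate with its 90% CI beside the confirmed rate, with the number of patients who differ and why.

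Patients who leave for palliative radiation (9.4) would be helped only by scans done before it; the unconfirmed rate shows the rest.

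**Cost.** The reconciling edits, a short addition to 16.21, one field on the event monitoring form and one line in the results table. Items 2 and 3 need no study-specific scans and no more patients. The downside is that routine-care scans may be less regular than protocol scans.

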 - Existence of a signed consent form
 - Existence of a signed authorization for use and disclosure of protected health information

- 6.5 At the time of registration, the following will be recorded:
- Patient has/has not given permission to store and use his/her sample(s) for future research of melanoma at Mayo Clinic.
 - Patient has/has not given permission to store and use his/her sample(s) for future research to learn, prevent, or treat other health problems.
- 6.6 Treatment cannot begin prior to registration and must begin ≤ 14 days after registration.
- 6.7 Pretreatment tests/procedures (see Section 4.0) must be completed within the guidelines specified on the test schedule.
- 6.8 All required baseline symptoms (see Section 10.6) must be documented and graded.
- 6.9a Treatment on this protocol must commence at Mayo Clinic Florida under the supervision of a medical oncologist.
- 6.9b Study drug is available on site.

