7.0 Protocol Treatment

7.1 Treatment Schedule - Use actual weight or estimated dry weight if fluid retention

Agent	Dose	Route	Day	ReRx
Pembrolizumab	200 mg	IV	Day 1	every 21 (+/- 3) days for a maximum of 2 years (approximately 35 cycles)
Imiquimod	5%	Cutaneous	M-F ^{a,b}	

a Regardless of what day of the week the cycle starts, imiquimod is to be administered daily for the remaining weekdays up to and including Friday.

b. At the completion of cycle 2 and cycle 4, a biopsy of the treated lesion will be performed (and if appropriate, a biopsy of an untreated lesion). Imiquimod is not to be administered the day of the biopsy or for six days following the biopsy. If the biopsy is performed on Monday, Imiquimod treatment should be given the following M-F. If the biopsy is performed on Tuesday, Imiquimod treatment should be given the next Tuesday-Friday and then M-F for the remainder of the cycle. If the biopsy is performed on Wednesday, Imiquimod treatment should be given the next Wednesday-Friday and then M-F for the remainder of the cycle. If the biopsy is performed on Thursday, Imiquimod treatment should be given the next Thursday-Friday and then M-F for the remainder of the cycle. If the biopsy is performed on Friday, Imiquimod treatment should be given the next Friday and then M-F for the remainder of the cycle.

- 7.2 Patients can be instructed in administration techniques of imiquimod and granted treatment independence. This training must be documented in medical record. Imiquimod is a commercial product dispensed from the pharmacy and is the same drug that would be prescribed to any other patient not on trial.
- 7.3 Imiquimod will be held for one week after biopsy to allow for proper wound healing.
- 7.4 If more than 1 cutaneous lesion is present, at least one lesion will not be treated with imiquimod to serve as a control for the effect of just pembrolizumab. The untreated lesion must be at least 2 cm from the treated lesion to account for possible treatment effect from the imiquimod on the primary.
- 7.5 Treatment by a local medical doctor (LMD) is not allowed.

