11.0 Treatment Evaluation Using RECIST 1.1 Guideline

11.1 The first scan after treatment initiation will be performed after the completion of cycle 4 (approximately week 12) and will be then performed every 12 weeks until disease progression is confirmed

Disease progression for this protocol is defined as meeting the RECIST criteria for disease progression on two consecutive evaluations at least 6 weeks apart (see Section 13.2).

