11.43 Response Criteria

11.431 All target lesions and target lymph nodes followed by CT/MRI/PET-CT/Chest X-ray/physical examination must be measured on re-evaluation at evaluation times specified in Section 11.1. Specifically, a change in objective status to either a PR or CR cannot be done without re-measuring target lesions and target lymph nodes.

Note: Non-target lesions and non-target lymph nodes should be evaluated at each assessment, especially in the case of first response or confirmation of response. In selected circumstances, certain non-target organs may be evaluated less frequently. For example, bone scans may need to be repeated only when complete response is identified in target disease or when progression in bone is suspected.

11.432 Evaluation of Target Lesions

- Complete Response (CR): All of the following must be true:
 - a. Disappearance of all target lesions.
 - b. Each target lymph node must have reduction in short axis to <1.0 cm.
- Partial Response (PR): At least a 30% decrease in PBSD (sum of the longest diameter for all target lesions plus the sum of the short axis of all the target lymph nodes at current evaluation) taking as reference the BSD (*see* Section 11.41).
- Progression (PD): At least one of the following must be true:
 - a. At least one new malignant lesion, which also includes any lymph node that was normal at baseline (< 1.0 cm short axis) and increased to ≥ 1.0 cm short axis during follow-up.

- b. At least a 20% increase in PBSD (sum of the longest diameter for all target lesions plus the sum of the short axis of all the target lymph nodes at current evaluation) taking as reference the MSD (Section 11.41). In addition, the PBSD must also demonstrate an absolute increase of at least 0.5 cm from the MSD.
- c. See Section 11.32 for details in regards to the requirements for PD via FDG-PET imaging.

- Stable Disease (SD): Neither sufficient shrinkage to qualify for PR, nor sufficient increase to qualify for PD taking as reference the MSD.

11.433 Evaluation of Non-Target Lesions & Non-target Lymph Nodes

- Complete Response (CR): All of the following must be true:
 - a. Disappearance of all non-target lesions.
 - b. Each non-target lymph node must have a reduction in short axis to <1.0 cm.
- Non-CR/Non-PD: Persistence of one or more non-target lesions or non-target lymph nodes.
- Progression (PD): At least one of the following must be true:

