16.4 Progression-free and overall survival

- 16.41 Progression-free survival time is defined as the time from registration to documentation of first disease progression or death due to any cause. Survival time is defined as the time from registration to death due to any cause.
- 16.42 The duration of response and the distributions of OS times and PFS times will be estimated using the Kaplan-Meier method.

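### Section 16.22 counts the time before any documented response as duration of response, and does not name death as an end event

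*Combined protocol and SAP*

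**What the plan says.** Section 16.22 limits the endpoint to patients with a PR or CR on two consecutive evaluations at least 12 weeks apart. For them, "the duration of treatment response is defined as the time from registration to disease progression". Death is not mentioned.

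Section 16.41 uses the same origin for PFS but a wider event: "Progression-free survival time is defined as the time from registration to documentation of first disease progression or death due to any cause". Section 16.42 then treats the endpoints alike: "The duration of response and the distributions of OS times and PFS times will be estimated using the Kaplan-Meier method". No censoring rule is given for duration of response, and no other section gives it a different start or adds death.

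Four provisions fix when a response can first be recorded:

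- Section 6.6: "Treatment cannot begin prior to registration and must begin ≤ 14 days after registration".
- Section 11.1: "The first scan after treatment initiation will be performed after the completion of cycle 4 (approximately week 12").
- Section 11.431: target lesions "must be measured on re-evaluation at evaluation times specified in Section 11.1", and a change of status to PR or CR requires that re-measurement.
- Section 4.0, footnote 4: later evaluations follow "approximately every 12 weeks) thereafter (±7days) until PD".

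Section 7.1 sets the cycle length: "every 21 (+/- 3) days for a maximum of 2 years".

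**The concern.** A duration of response should measure how long a response lasts once it is there. Here the clock starts before treatment does. The stretch up to the first documented response is one in which a confirmed responder cannot, by selection, have progressed, so it adds event-free time to every responder. The end of the interval also differs from PFS, because a responder's death without recorded progression is not named as a failure.

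Both features act in the same direction. Durability carries weight in this protocol: the background describes most pembrolizumab responses as durable, and Section 1.73 cites remissions of 9-12 months in two patients given ipilimumab with imiquimod. Twelve added weeks are 12/52 = 23% to 12/39 = 31% of such a period.

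**Working it through.** **1. The plan's own timing.** Four cycles of 21 days are 4 × 21 = 84 days = 12.0 weeks, which agrees with the stated week 12.

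**2. Earliest documented response, counted from registration.** Inputs: start delay 0 to 14 days (6.6), scan window ±7 days (4.0, taken to cover the first scan too), cycle window ±3 days (7.1).

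- Nominal: 84/7 = 12.0 weeks.
- Scan window only, no start delay: (84 − 7)/7 = 11.0 weeks.
- Cycles also at 18 days: (4 × 18 − 7)/7 = 9.3 weeks.
- 14-day delay and late scan: (14 + 84 + 7)/7 = 15.0 weeks.
- Cycles also at 24 days: (14 + 4 × 24 + 7)/7 = 16.7 weeks.

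**3. Effect of the origin.** Let R be the time from registration to first documented response and P the time from registration to progression. Section 16.22 reports P, while the time from response is P − R. The excess is R and the ratio is P/(P − R). Nominal weeks, no start delay:

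| First response (R) | PD (P) | Reported under 16.22 | From first response | Ratio |
|---|---|---|---|---|
| 12 | 36 | 36 | 24 | 1.50 |
| 12 | 60 | 60 | 48 | 1.25 |
| 12 | 156 | 156 | 144 | 1.08 |
| 24 | 48 | 48 | 24 | 2.00 |
| 24 | 60 | 60 | 36 | 1.67 |
| 36 | 60 | 60 | 24 | 2.50 |

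Week 156 is the 3-year follow-up limit in Section 4.1 (3 × 52).

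**4. Effect of leaving out death.** The documents give no rate of death without documented progression, so this step is an illustration. Assume exponential times from response, a median M to progression or death, a share s of first events that are deaths without progression, and censoring of those deaths. The total hazard is ln 2/M and the progression hazard is (1 − s) ln 2/M, so the estimated median becomes M/(1 − s). With M = 52 weeks:

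| s | Median, deaths censored | Plus 12 weeks from the origin |
|---|---|---|
| 10% | 52/0.9 = 57.8 | 69.8 |
| 20% | 52/0.8 = 65.0 | 77.0 |
| 30% | 52/0.7 = 74.3 | 86.3 |

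The multiplier 1/(1 − s) does not depend on M. It is 1.11, 1.25 and 1.43 for these shares.

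**5. Relation to PFS.** The two endpoints share an origin. In a responder with recorded progression they give the same time if both use the same PD date. The plan leaves that open: PFS refers to first progression, whereas Section 11.1 defines progression as PD on two evaluations at least 6 weeks apart. If duration used the confirmed date and PFS the first, duration would run about 6 weeks longer in the same patient.

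**6. Number of patients.** At the single-agent response rates in Section 1.9c11, 10 × 0.25 = 2.5 to 10 × 0.40 = 4 patients would contribute.

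**The case against.** The best defence is about reach. This is a 10-patient pilot seeking preliminary data. Duration of response is not named in the primary goal, drives neither the 25.9% bound in Section 16.1 nor the stopping rule in 16.61, and enters no test or planned comparison. The definition is stated openly and shares its origin with PFS and OS. If responses are as durable as the background expects, the relative excess is small. All of this stands. It limits severity but does not make the quantity a duration of response.

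Several stronger readings are tempting, and the documents do not support them:

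- *Twelve weeks is a hard minimum.* It is nominal; the visit windows allow about 11 weeks, or about 9 at the extreme.
- *The plan orders deaths to be censored.* It is silent. Censoring is the natural Kaplan-Meier reading of an event defined as progression only. Section 11.45 also records symptomatic deterioration as PD, so some of these deaths would already count as progression.
- *The endpoint is exactly PFS with deaths removed.* That needs a common PD date, which the plan does not fix.
- *The endpoint adds no information.* PFS covers all evaluable patients and 16.22 only confirmed responders, so the two curves differ.
- *The whole event-free stretch to about week 24 comes from the origin.* About 12 of those weeks come from requiring confirmation, and they remain under the repaired definition.

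One could add that a response seen at week 12 may have begun earlier. That may be so, but no disease evaluation is scheduled before then that could date it.

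**Conclusion.** The concern holds. As written, every responder's reported duration includes the time from registration to first documented response: nominally 12 weeks, 24 if first seen at the second scan, more if later. The overstatement ranges from 1.50 times for PD at week 36 to 1.08 times at week 156 when response is first seen at week 12, and it is larger for later responses. This part rests only on the plan's own definitions and schedule.

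The omission of death biases the estimate further upward if such deaths are censored. Its size depends on how many responders die without recorded progression, which the documents do not tell us; the figures above are illustrative. The measure is then essentially PFS time restricted to confirmed responders, without death as an event.

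Severity is moderate. The estimate is descriptive, rests on perhaps 2 to 4 patients and decides nothing in the trial, but it would be misread as durability.

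**What to change.** Redefine the endpoint in Section 16.22. For patients with a confirmed response, duration runs from the first evaluation documenting the CR or PR that was later confirmed, to progression or death from any cause, whichever is earlier. Patients alive without progression are censored at their last disease evaluation.

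In the same amendment, state whether the first or the confirmed PD date is the event date, and use that date for PFS in 16.41 too. The confirmation interval for response also needs reconciling, because Section 1.9c11 gives 6 weeks and Section 16.2 gives 12, and this decides who enters the analysis.

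No new data are needed: the evaluations in Section 4.0 and the survival follow-up in Section 4.1 already supply the dates. The cost is a short amendment and shorter reported durations.
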